6.14.2.2. Deaths, Other Serious Adverse Events and Other Notable Adverse Events

The number and percentage of patients reported with an SAE during the treatment period will be summarized by treatment using MedDRA PT. A listing of SAEs will be provided.

The number and percentage of patients who permanently discontinued from study treatment due to an AE (including AEs that led to death) during the treatment period will be summarized by treatment using MedDRA PT. Events will be ordered by decreasing frequency in the all treatment groups.

6.14.3. Clinical Laboratory Evaluation

As described more fully in compound level safety standards and in the laboratory-related PhUSE white papers (PhUSE 2013; PhUSE 2015), the clinical laboratory evaluations will be summarized as described in [Table KGAB.6.14](#). Hormone analytes are summarized/plotted similarly for adolescent patients.

Table KGAB.6.14. Analysis for Clinical Laboratory Evaluations

Analysis	Population
Box plots of observed values by visit Box plots for change values by visit	S, M
Change from baseline to last observations. ANCOVA model with treatment and baseline value in the model.	S, M
Scatter plots of baseline-by-maximum values and baseline-by-minimum values	S, M
Treatment-emergent abnormal high lab values (i.e., patients shifting from a normal/low maximum baseline value to a high maximum postbaseline value) or abnormal low lab values (i.e., patients shifting from normal/high minimum baseline value to a low minimum postbaseline value)	S, M, A
Shift tables showing the number of patients who shift from each category of maximum (minimum) baseline observation to each category of maximum (minimum) postbaseline observation. Here categories may be low, normal, or high with cut-offs defined in the compound level safety standards.	S, M
Listing of abnormal findings for laboratory analyte measurements, including qualitative measures	All Enrolled

Abbreviations: A = All Lebrizumab Safety Population; ANCOVA = analysis of covariance; M = Maintenance Primary Population; S = Safety Population.

6.14.4. Vital Signs and Other Physical Findings

As described more fully in compound level safety standards and in the laboratory-related PhUSE white papers (PhUSE 2013; PhUSE 2015), vital signs will be summarized similarly to the clinical laboratory evaluation (Table KGAB 6.15). For vital signs, treatment emergent low and high are based on a combination of a specified value and a change or percentage change for adults and adolescents as defined in the compound level safety standards.

Table KGAB 6.15. Analysis Related to Vital Signs

Analysis	Population
Box plots for observed values by visit	S, M
Box plots for change from baseline values by visit	S, M
Scatterplots of baseline-by-maximum values and baseline-by-minimum values	S, M
Tables with the number and percentage of subjects who shift from normal/high to low (i.e., treatment-emergent low) and the number and percentage of subjects who shift from normal/low to high (i.e., treatment-emergent high); the limits are defined in the compound level safety standards	S, M, A

Abbreviations: A = All Lebrizumab Safety Population; M = Maintenance Primary Population; S = Safety Population.

6.14.4.1. Adolescent Standardized Growth

Weight, height, and BMI data will be merged to the Centers for Disease Control and Prevention (CDC) standard growth data (released in 2000) by age and gender in order to compare patients' growth with the standard. Z-score and standardized percentile of weight, height, and BMI at each visit will be calculated and compared to the 2000 CDC growth charts. Because of the short duration of controlled period, only All Lebrizumab Safety Population will be described during Combined Induction and Maintenance Periods.

The z-score and percentile calculations are based on algorithms and data provided by the National Center for Health Statistics. The details are provided in the CDC website (<https://www.cdc.gov/nccdphp/dnpao/growthcharts/resources/sas.htm>) (CDC resources page [WWW]).

The following summaries and plots will be provided:

Table KGAB.6.16. Analysis Related to Adolescent Standardized Growth

Analysis	Population
Summaries for baseline, mean change of actual measure, z-score and standardized percentile of weight, height, and BMI.	A
Scatter plot of patients' mean weight, height, and BMI standardized percentile versus lebrizumab exposure time	A

Abbreviations: A = All Lebrizumab Safety Population; BMI = body mass index.

6.14.5. Immunogenicity

An individual sample is potentially examined multiple times in a hierarchical procedure to produce a sample anti-drug antibody (ADA) assay result and may yield a sample neutralizing ADA (NAb) assay result. Treatment-emergent ADA (TE-ADA) are defined as those with a titer 2-fold (1 dilution) greater than the minimum required dilution if no ADAs were detected at baseline (treatment-induced ADA) or those with a 4-fold (2 dilutions) increase in titer compared to baseline if ADAs were detected at baseline (treatment-boosted ADA). A patient is considered TE-ADA positive when at least 1 postbaseline ADA sample meets the definition of TE-ADA.

Compound level safety standards will be followed in the analyses of immunogenicity. Listings of immunogenicity assessments will be provided for the Safety Population. The summary of TE-ADA and NAb status will be produced for the Safety Population during the Induction Period. The summary for Maintenance Primary Population will be provided for the combined Induction and Maintenance Periods. For the Maintenance Primary Population, the immunogenicity analysis will be cumulative across both the Induction and Maintenance Periods. Additional assessments of the relationship between immunogenicity and efficacy and TEAE by TE-ADA status will be performed as part of the integrated analysis including other Phase 3 lebrizumab AD trials.

6.14.6. Special Safety Topics including Adverse Events of Special Interest

This section includes areas of interest whether due to observed safety findings, potential findings based on drug class, or safety topics anticipated to be requested by a regulatory agency for any reason. In general, potential adverse events of special interest (AESI) relevant to these special safety topics will be identified by one or more Standardized MedDRA Query(ies) (SMQs), by a Lilly-defined MedDRA PT listing based upon the review of the most current version of MedDRA, or by treatment-emergent relevant laboratory changes, as described below. Additional special safety topics may be added as warranted.

Unless otherwise specified, the special safety topics will be summarized for the Safety Population and All Lebrizumab Safety Population during their associated study periods as described in Section 6.14. Additional safety analysis may be added as needed.

Full details of the search terms and rules for deriving special safety topics in each of the sections below are described in the compound level safety standards along with information about the types of summaries and listings to be provided. In the event that the listing of terms or analysis changes for a special safety topic, it will be documented in the compound level safety standards which will supersede this document; it will not warrant an amendment to the individual study SAP.

6.14.6.1. Hepatic Safety

Hepatic labs include alanine aminotransferase (ALT), aspartate transaminase (AST), total bilirubin (TBL), and serum alkaline phosphatase (ALP).

Table KGAB.6.17. Summary Tables Related to Hepatic Safety

Analysis	Population
ALT and AST: The number and percentage of subjects with a measurement greater than or equal to 3 times (3X), 5 times (5X), and 10 times (10X) the performing lab upper limit of normal (ULN) during the treatment period for all subjects with a post-baseline value and for subsets based on various levels of baseline value TBL and ALP: The number and percentage of subjects with a measurement greater than or equal to 2 times (2X) the performing lab ULN during the treatment period will be summarized for all subjects with a post-baseline value and for subsets based on various levels of baseline value	S, A
Plot of maximum post-baseline ALT vs. maximum post-baseline total bilirubin	Safety Population for All Periods: ever on lebri and never on lebri

Abbreviations: A = All Lebrikizumab Safety Population; ALP = serum alkaline phosphatase; ALT = alanine aminotransferase; AST = aspartate transaminase; lebri = lebrikizumab; S = Safety Population; TBL = total bilirubin.

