**Study Design:**

This is a randomized, double-blind, placebo-controlled, parallel-group study which is 52 weeks in duration. The study is designed to confirm the safety and efficacy of lebrikizumab as monotherapy for moderate-to-severe atopic dermatitis utilizing a 16-week induction treatment period and a 36-week long-term maintenance treatment period.

Eligible adult and adolescent ( $\geq 12$  to  $< 18$  years weighing  $\geq 40$  kg) patients with moderate-to-severe atopic dermatitis for at least one year, defined according to the American Academy of Dermatology Consensus Criteria, an Eczema Area and Severity Index Score (EASI) of  $\geq 16$ , an Investigator Global Assessment (IGA) score of  $\geq 3$  and a body surface area (BSA) of  $\geq 10\%$  will be enrolled.

During the 16-week Induction Period, approximately 400 patients will be stratified and randomized 2:1 to either 250 mg lebrikizumab (loading dose of 500 mg given at Baseline and Week 2) or placebo by subcutaneous (SC) injection every 2 weeks (Q2W). All study drug injections will be administered in the clinic.

After completion of the Week 16 visit, patients who have responded to treatment [defined as having an IGA of 0 or 1 or a 75% reduction in EASI from Baseline to Week 16 (EASI-75)] will enter the Maintenance Period and will be re-randomized 2:2:1 to one of the following treatment groups: lebrikizumab 250 mg Q2W, lebrikizumab 250 mg given every four weeks (Q4W), or placebo Q2W. Patients will be instructed to self-administer study drug at home.

Responders who received placebo during the first 16 weeks of the study and who are re-randomized to lebrikizumab arms will receive a loading dose of lebrikizumab of either 500 mg given at Week 16 or 500 mg given at Weeks 16 and 18, based on the active treatment group assigned in Maintenance.

Patients who do not achieve an IGA of 0 or 1 or an EASI-75 at Week 16, and those patients not maintaining an EASI-50 response following re-randomization at Week 24, 32, 40 or 48, will be assigned to an Escape Arm and receive lebrikizumab 250 mg as long-term treatment Q2W through Week 52. Patients not achieving an EASI-50 response after 8 weeks of treatment in the Escape Arm will be terminated from the study.

Efficacy will be measured through the IGA, EASI, BSA, SCORAD, Pruritus and Sleep-loss scores.

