**5.3.3. Escape Arm**

Patients who require topical or systemic rescue treatment (Section 6.3) for atopic dermatitis during the Induction Period, or, are non-responders at Week 16, will be eligible for treatment in an Escape Arm where patients will receive lebrikizumab Q2W from Week 16 through Week 52. In addition, patients who do not maintain an acceptable response during the Maintenance Period (have an EASI score <50% of baseline), will be eligible for the Escape Arm.

To enter the Escape Arm, patients must have been compliant with study visits during the Induction Period or the Maintenance Period, respectively. Patients receiving systemic rescue medication (Section 6.3) will be required to washout for 5 half-lives prior to initiating treatment in the Escape Arm. All patients eligible for the Escape Arm will receive blinded loading doses, based on their prior treatment assignment (see Table 3 below), followed by 250 mg lebrikizumab Q2W through Week 52 on study in an open-label fashion. Patients in the Escape Arm must

comply with study visits every 4 weeks. Patients in the Escape Arm, not achieving or maintaining an EASI50 score after 8 weeks of treatment will be terminated from the trial.

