#### **7.6. Week 8 ( $\pm$ 3 Days)**

- Administer the DLQI/CDLQI
- Complete the following assessments: IGA, BSA and EASI
- Review and record AEs and update concomitant medication and procedure/therapy information
- Review compliance report on the eDiary, confirm moisturizer use and remind patient to record the following: Pruritus and Sleep-Loss (daily), and POEM (weekly)
- Measure vital signs
- Draw blood samples for laboratory tests, except hormones

- Collect a urine sample for urinalysis
- Conduct urine pregnancy test (WOCBP only)
- Administer study drug

Sites collecting photos will also:

- Obtain photographs of the target lesion

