5.1.3. Maintenance Period (Week 16 to Week 52 [36 Weeks])

5.1.3.1. Maintenance Blinded Period

After completion of the Week 16 visit, patients who have responded to treatment (defined as having an IGA of 0 or 1 or a 75% reduction in EASI from Baseline to Week 16 [EASI-75] according to IWRS system) will enter the Maintenance Period and will be re-randomized 2:2:1 to one of the following treatment groups: lebrikizumab 250 mg Q2W, lebrikizumab 250 mg Q4W, or placebo Q2W. Throughout the maintenance blinded period, patients will receive placebo, as appropriate, to maintain the study blind across treatment groups.

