5.1.3.2. Maintenance Escape Period

[figure not shown]
Patients who do not achieve an IGA of 0 or 1 or an EASI-75 at Week 16, patients received topical or systemic rescue therapy between baseline to Week 16 and those patients not maintaining an EASI-50 response following re-randomization at Week 24, 32, 40, or 48 will be

assigned to an Escape Arm and receive lebrikizumab 250 mg as open-label treatment Q2W through Week 52. Patients not achieving an EASI-50 response in the Escape Arm after 8 weeks of treatment will be terminated from the study.

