6.1.1. Analysis Populations

Analysis populations are defined in [Table KGAB.6.1](#) along with the analysis they will be used to conduct. [Table KGAB.6.2](#) describes the treatment groups and the comparisons for each study period and the analysis population.

[Figure KGAB.6.1](#) shows a pictorial description of all the analysis populations.

[figure not shown]

Figure KGAB.6.1. Study periods and analysis populations.

Table KGAB.6.1. Analysis Populations

Population	Description
All Entered Patients	All patients who signed informed consent. Patient flow will be summarized.
Intent-to-Treat (ITT) Population	All randomized patients, even if the patient does not take the assigned treatment, does not receive the correct treatment, or otherwise does not follow the protocol. Patients will be analyzed according to the treatment to which they were assigned. Unless otherwise specified, efficacy and health outcomes analyses for the Induction period will be conducted on this population.
Safety Population	All randomized patients who received at least 1 dose of study treatment during Induction Period. Safety analyses for Induction period will be conducted on this population.
Maintenance Primary Population (MPP)	All patients who were randomized to Lebrikizumab 250 mg Q2W at Baseline Visit and re-randomized to Lebrikizumab 250 mg Q2W, Lebrikizumab 250 mg Q4W or placebo at Week 16 and received at least 1 dose of study treatment during the maintenance period. Patients will be analyzed according to the treatment to which they were re-randomized. Only information prior to escape will be presented. Efficacy, health outcomes, and safety analyses for the maintenance period will be conducted on the Maintenance Primary population
Maintenance Secondary Population (MSP)	Including patients who were randomized to placebo at Baseline Visit and re-randomized to Lebrikizumab 250 mg Q2W, Lebrikizumab 250 mg Q4W or placebo at Week 16, and received at least one dose of study treatment during the maintenance period. Selective efficacy analyses for the maintenance period will be conducted on the Maintenance Secondary Population. Patients will be analyzed according to the treatment to which they were re-randomized. Only information prior to escape will be presented.

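### The only joint ALT–bilirubin plot listed in the SAP compares ever with never on lebrikizumab over all periods, which leaves a very small, non-randomised comparator and sets no window for values taken on placebo

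*SAP*

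**What the plan says.** SAP 6.14.6.1, Table KGAB.6.17, has two rows. The first counts patients above multiples of the upper limit of normal, separately for ALT, AST, total bilirubin and alkaline phosphatase, in the Safety Population and the All Lebrikizumab Safety Population. The second is the "Plot of maximum post-baseline ALT vs. maximum post-baseline total bilirubin", and its population entry is "Safety Population for All Periods: ever on lebri and never on lebri".

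The Safety Population (SAP 6.1.1) is "All randomized patients who received at least 1 dose of study treatment during Induction Period", so it includes the placebo arm. For laboratory values, SAP 6.1.2 ends the baseline period at the first Induction injection. SAP 6.1.4 moves the baseline to Week 16 for patients first exposed in Maintenance, but says so only for treatment-emergent adverse events, and refers further baseline detail to the Compound Level Safety Standard.

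Patient flow at Week 16 is as follows. Responders are "re-randomized 2:2:1 to one of the following treatment groups: lebrikizumab 250 mg Q2W, lebrikizumab 250 mg Q4W, or placebo Q2W" (SAP 5.1.3.1). Non-responders and rescued patients are "assigned to an Escape Arm and receive lebrikizumab 250 mg as open-label treatment Q2W through Week 52" (SAP 5.1.3.2). Re-randomised patients who lose EASI-50 at Week 24, 32, 40 or 48 go the same way.

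**The concern.** A joint plot is read for patients with both analytes raised, and for whether such patients are more common on drug than on control. Here the patient is labelled by eventual exposure, while the plotted maximum may come from any period. Two things follow from the text as it stands.

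- The control group consists of placebo patients who left early, plus the few placebo responders who stayed on placebo throughout. It is small, self-selected and mostly observed for a short time.
- A joint elevation at Week 8, or in the pre-dose Week 16 sample, in a patient still on placebo would appear as an ever-on-lebrikizumab point if that patient later crossed over.

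No other ALT-with-bilirubin display is listed in the SAP. The general laboratory displays in Table KGAB.6.14 are not specified jointly for the two analytes.

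**Working it through.** **Plan figures.** The documents give no size for the ever and never groups, so there is no stated figure to reproduce for this point. The response rates used below come from SAP 5.2 and do reproduce the power stated there. With 96 vs 48 patients and a continuity-corrected chi-square test, power is about 95.1% for IGA (34.7% vs 7.7%) and 99.6% for EASI-75 (48.0% vs 11.5%); the plan says more than 95%.

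**Inputs.**
- Enrolment: "approximately 400 patients will be stratified and randomized 2:1" (Protocol synopsis), giving a placebo arm P = 400/3 ≈ 133 and a lebrikizumab arm of about 267.
- Placebo responder share r. A responder has IGA 0/1 or EASI-75. With placebo rates of 7.7% and 11.5%, r lies between 11.5% (full overlap) and 7.7% + 11.5% = 19.2% (no overlap). These rates already count rescued patients as non-responders.
- Share of placebo responders kept on placebo: 1/5, from 2:2:1.
- Share d of the placebo arm leaving before Week 16: not in the documents, so assumed at 0–20%.

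**Crossover among those who reach Week 16.** This is 1 − r/5: 1 − 0.115/5 = 97.7% and 1 − 0.192/5 = 96.2%. Even with r = 30% it is 94%.

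**Size of the never group.** Never = P·d + P·(1 − d)·r/5. In each range below, one end is r = 11.5% and the other r = 19.2%.

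| d | Early leavers, P·d | Placebo throughout, P·(1−d)·r/5 | Never | Placebo arm moved to ever | Early leavers within never |
|---|---|---|---|---|---|
| 0% | 0 | 3.1–5.1 | 3–5 | 96–98% | 0% |
| 5% | 6.7 | 2.9–4.9 | 10–12 | 91–93% | 58–70% |
| 10% | 13.3 | 2.8–4.6 | 16–18 | 87–88% | 74–83% |
| 20% | 26.7 | 2.5–4.1 | 29–31 | 77–78% | 87–92% |

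For example, with d = 10% and r = 11.5%: 13.3 + 133.3 × 0.90 × 0.115/5 = 13.3 + 2.8 = 16.1.

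**Composition of the ever group.** The share randomised to placebo is (P − never)/(400 − never). At d = 10% and r = 11.5% this is 117.2/383.9 = 31%. Over the whole grid it is 28–33%.

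**Which values are affected.** Protocol Appendix 1 schedules post-baseline chemistry at Weeks 8, 16, 32 and 52. Protocol 7.6 covers Week 8 ("Draw blood samples for laboratory tests, except hormones"), and Protocol 7.10 makes the Week 16 sample pre-dose. A placebo patient who crosses over at Week 16 and is followed to Week 52 therefore has two of four scheduled values taken before any lebrikizumab. All four fall after the baseline defined in SAP 6.1.2.

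**The case against.** **The randomised comparison is still there.** A reader might infer that the controlled 16-week liver comparison has been thrown away. The documents do not support that. The first row of Table KGAB.6.17 covers the Safety Population, which SAP 6.14 ties to the Induction Period and Table KGAB.6.2 compares by randomised arm. Table KGAB.6.14 adds box plots, ANCOVA of change, scatter plots and shift tables for the same population. This objection stands: only the joint display lacks a randomised comparison.

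**The window may be set elsewhere.** A reader might also take it as settled that placebo values will be plotted as lebrikizumab values. No sentence says so for this plot. SAP 6.14.6 places the derivation rules for special safety topics in the compound level safety standards and lets those supersede the SAP. The SAP elsewhere follows exposure: in the baseline rule of 6.1.4, and in the exposure calculation of 6.14.1, which starts at the first lebrikizumab injection and leaves out Maintenance time on placebo. The plot may be meant to work the same way. This stands as a limit on certainty. It does not help the comparator, because a window leaves the never group just as small.

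**The plot is descriptive.** No test or decision rule hangs on it, abnormal laboratory findings are listed for enrolled patients, and the DSMB reviews safety separately. That limits the harm, but a reader of the plot would still lack a like-for-like control.

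**The numbers are conditional.** Drop-out before Week 16 sets most of the never group's size and is assumed. Protocol 5.3.3 says of escape that "patients will receive lebrikizumab Q2W from Week 16 through Week 52", but makes patients eligible subject to visit compliance, so a few who reach Week 16 may not cross over. The two-of-four count should not be extended to every crossed-over patient, since Escape Arm patients without EASI-50 after 8 weeks are terminated and may have no Week 32 or Week 52 sample.

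**Conclusion.** The point holds for the joint plot and no further. Followed as written, the row compares nearly all the trial's patients with about 3–31 never-exposed ones, against 133 randomised to placebo. The range covers assumed drop-out of 0–20% and a responder share of 11.5–19.2%. From 5% drop-out upward, most of the never group left before Week 16; later transfers at Weeks 24–48 shrink it further. About 28–33% of the ever points belong to patients randomised to placebo.

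That their placebo-period values enter those points is the natural reading of an all-periods maximum combined with the Induction baseline. It remains conditional on the compound level safety standards. If a restriction exists there, the SAP row should state it. The small, non-randomised comparator does not depend on that document.

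**What to change.** In Table KGAB.6.17:

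1. Add an ALT–bilirubin plot for the Induction Period, Safety Population, by randomised arm (about 267 vs 133), using maximum values through the pre-dose Week 16 sample.
2. Keep the all-periods plot, but for lebrikizumab-exposed patients count only values after their first lebrikizumab injection. Re-set baseline for those first exposed in Maintenance, as 6.1.4 already does for treatment-emergent adverse events.
3. Show Maintenance values of patients kept on placebo after placebo induction in a separate panel or listing. Simply dropping the never group would lose them.
4. State the window in the row itself, or cite the clause of the compound level safety standards that sets it.

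The cost is one extra plot, a small panel or listing, and a data filter in the program. No new data are needed. SAP version 4 was approved after the study team was unblinded to induction treatment, so the added Induction plot should be recorded as a later, descriptive addition.
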